#### 1.7.3 Measurement of circulating tumor cells pre- and post-treatment, and correlation with tumor response and time to progression.

Circulating tumor cells (CTC) have been detected in peripheral blood in patients with epithelial tumors, including metastatic breast, colon, and prostate cancer. Recent data suggests that the presence of CTC can be predictive and prognostic, and the CellSearch assay platform has been approved by the FDA to collect CTC before and after therapy, and assess response to treatment (37-38). However, aside from high associated costs, this assay depends on enrichment of CTC based on their expression of EpCAM, a variably expressed cell surface marker, adversely affecting CTC enrichment. It is also likely that enumeration of CTCs alone may be inadequate as prognostic and predictive marker for clinical outcome and response to therapy; particular biomarkers expressed on CTCs may provide a wealth of additional information.

Importantly, although the utility of CTC analysis in other common malignancies has been widely demonstrated, very few studies have looked for circulating tumor cells in sarcoma patients and there are no studies evaluating their prognostic or predictive impact. Previous reports have detected Ewing sarcoma CTC in blood and bone marrow using flow cytometry to isolate CD99+CD45- cells (39-40). Most recently, Satelli et al demonstrated that CTC with cell surface vimentin expression were detectable in human peripheral blood samples from patients with osteosarcoma, undifferentiated pleomorphic sarcoma, leiomyosarcoma, Ewing's

sarcoma, and angiosarcoma (41). Interestingly, patients with primary tumors had fewer CTC than patients with metastatic tumors.

Utilizing a unique, microfabricated parylene membrane-based device in collaboration with [name] (42), we are currently collecting CTCs at various timepoints in sarcoma patients exploring whether CTC could serve as a marker of early micrometastatic disease in sarcomas, and may portend worse prognosis as seen in other tumor types. Effects on circulating tumor cells are particularly interesting in light of immunotherapy, in hopes that a more effective CD8+ T-cell anti-tumor effect could decrease the presence of circulating tumor cells and decrease development of new metastatic sites. Thus, peripheral blood samples will be drawn at selected timepoints and filtered to detect the numbers of circulating tumor cells using this technology. The presence or absence of CTC will be correlated with tumor response.

## 2.0 OBJECTIVES

### 2.1 Primary Objective

- To estimate progression-free survival rate at 3 months after concurrent axitinib and pembrolizumab therapy in patients with alveolar soft part sarcoma and other advanced soft tissue sarcomas.

### 2.2 Secondary Objectives

- To estimate the objective response rate (ORR), clinical benefit rate (CBR), and progression-free survival (PFS) using RECIST 1.1, as well as overall survival (OS) in patients with ASPS and other advanced soft tissue sarcomas treated with concurrent axitinib and pembrolizumab.
- To describe the safety and toxicity profile of axitinib with inpatient dose titration combined with pembrolizumab therapy in patients with ASPS and other advanced soft tissue sarcomas.

### 2.3 Exploratory Objectives

- To identify associations between clinical benefit status (CR/PR/SD vs. PD) and a) T-cell infiltration; b) PD-1, PD-L1, PD-L2, TIM3, LAG3, and CTLA-4 expression categories in tumor tissue.
- To identify associations between progression-free status at 3 months (no progression vs. progression) and a) T-cell infiltration; b) PD-1, PD-L1, PD-L2, TIM3, LAG3, and CTLA-4 expression categories in tumor tissue.
- To identify associations between clinical benefit status (CR/PR/SD vs. PD) and the absolute change (baseline to cycle 3, baseline to off-study, and cycle 3 to off-study) in each of the following T-cell subsets in peripheral blood and tumor tissue: (CD8+,

CD4+, T-regulatory, memory phenotype, naïve phenotype, Ki67+, PD-1+, TIM3+, LAG3+, CTLA4+).

- To identify associations between progression-free status at 3 months (no progression vs. progression) and the absolute change (baseline to cycle 3, baseline to off-study, and cycle 3 to off-study) in each of the following T-cell subsets in peripheral blood and tumor tissue: (CD8+, CD4+, T-regulatory, memory phenotype, naïve phenotype, Ki67+, PD-1+, TIM3+, LAG3+, CTLA4+).
- To identify associations between the progression-free status at 3 months (no progression vs. progression) and the change in genomic expression of angiogenesis and immune-related genes, as assessed by RNA expression in tumor biopsies and peripheral blood samples (collaboration with Nanostring, Simpatica Medicine).
- In expansion cohort of ASPS patients, to identify associations between the progression-free status at 3 months (no progression vs. progression) with T cell clonal populations in tumor biopsies and peripheral blood cells.

To identify plasma angiogenic activity at baseline, cycle 1 day 8 representing axitinib monotherapy (ASPS expansion cohort only), and cycle 3 day 1.

- To describe the relationship between tumor response according to RECIST 1.1 and tumor response according to alternative radiologic methods including: a) Choi criteria, b) immune-related response criteria (irRC), c) MRI volumetrics, and d) PERCIST 1.0.
- To identify associations between clinical benefit status (CR/PR/SD vs. PD) by RECIST 1.1 and the absolute change (baseline to cycle 3, baseline to off-study, and cycle 3 to off-study) in quantity of circulating tumor cells (CTCs).
- To identify associations between the progression-free status at 3 months (no progression vs. progression) and the absolute change (baseline to cycle 3, baseline to off-study, and cycle 3 to off-study) in quantity of circulating tumor cells (CTCs).

### 3.0 ENDPOINTS

#### 3.1 Primary endpoint

- The progression-free survival by RECIST v1.1 of sarcoma patients treated with concurrent axitinib/pembrolizumab therapy.

Evaluable criteria:

Eligible subjects enrolled into the study that received 80% of scheduled axitinib doses and two infusions of pembrolizumab, have measurable disease at baseline and at least one post-baseline disease assessment.

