### 3.2 Secondary endpoints

- The objective response (CR/PR), clinical benefit (CR/PR/SD), time to progression (TTP), and overall survival (OS) defined as time from study treatment initiation to first occurrence of progression by RECIST v1.1 or death of sarcoma patients treated with concurrent axitinib/pembrolizumab therapy.

Evaluable criteria:

Eligible subjects enrolled into the study that received at least 80% of scheduled axitinib doses and two infusions of pembrolizumab, have measurable disease at baseline and at least one post-baseline disease assessment.

- Adverse events, including dose-limiting toxicity and serious adverse events (grade 3 or 4) will be graded using NCI CTCAE version 4.03.

Evaluable criteria:

Eligible subjects enrolled into the study that receive at least one dose of both axitinib and pembrolizumab. Patients who withdraw from the study prior to week 2 for any reason other than DLT or other significant toxicity will not be considered evaluable for toxicity.

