### 12.1 Pre-Treatment Evaluation (Screening)

The following must be collected/ performed within  $\leq 28$  days prior to Cycle 1, day 1 of treatment. Clinical and laboratory evaluations performed as part of routine standard of care do not need to be repeated if performed within the appropriate window.

- Demographics: The age, race, ethnicity and gender of each patient
- Medical history: Relevant medical history including background and progress of the malignancy and description of all prior therapies
- Physical examination (PE): A complete PE will include assessments of general appearance, skin, head (eyes, ear, nose, and throat), neck, lungs, heart, abdomen, back, lymph nodes, extremities, and neurological exam
- ECOG Performance Status (ECOG PS) will be assessed as specified in Appendix C
- Height
- Weight
- Vital signs (V/S): Vital signs measurements include: diastolic blood pressure (BP) and systolic BP, heart rate (HR), respiratory rate (RR), oral temperature (oral temp) and oxygen saturation (O2)
- Complete Blood Count (CBC): CBC evaluations with differential and platelets
- Comprehensive Metabolic Panel (CMP): CMP evaluations to include magnesium, phosphate, and direct bilirubin
- Coagulation studies: PT/ (INR), aPTT
- Thyroid Function Tests (TFTs): Thyroid stimulating hormone (TSH), thyroxine (free T4), and triiodothyronine (T3)
- Urine pregnancy test: A pregnancy test will be performed for women of childbearing potential (WOCBP) at screening and throughout the study.
- Urinalysis: A urinalysis with microscopic analysis (UA micro) will be performed at Screening. Any patient with 1+ or greater protein screen without evidence of infection or contaminated sample must have urine microalbumin and/or 24 hour urine creatinine clearance to document proteinuria.
- 12-lead Electrocardiogram (ECG)
- 2D Echocardiogram (ECHO)
- Imaging studies for tumor assessment (CT and/or MRI of all known sites of disease): the same method of assessment and technique should be used at baseline and during treatment and follow-up
- Correlative studies:
  - PET/CT

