### **14.2 Progression-Free Survival (PFS)**

Patients will be evaluated during treatment and by follow-up assessments post-treatment at: 30-days (+5 days). PFS is defined as the time from treatment initiation until documented disease progression or death (by any cause, in the absence of progression). In progression-free patients, PFS will be censored at the last evaluable tumor assessment (RECIST v1.1).

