#### Endpoints

The primary endpoint will be the progression-free survival by RECIST 1.1 in evaluable patients treated with combination axitinib/pembrolizumab.

The secondary endpoints include:

- The objective response rate (ORR) is defined as the proportion of patients whose response by RECIST 1.1 is complete response (CR) or partial response (PR). The clinical benefit rate (CBR) is the proportion of patients whose response by RECIST 1.1 is complete response (CR), partial response (PR), or stable disease (SD). The time to progression (TTP) is defined as time from treatment initiation to first occurrence of progression by RECIST v1.1 or death of sarcoma patients treated with concurrent axitinib/pembrolizumab therapy. Overall survival (OS) is defined as the elapsed time from treatment initiation to death from any cause, whichever is earlier. Patients alive or those lost to follow-up will be censored at the last date of contact (or last date known to be alive).
- Adverse events, including dose-limiting toxicity and grade 3 or grade 4 serious adverse events
  - DLT includes treatment-related (possible, probably, or definite) grade 3 or higher toxicities as detailed in section 7.2. Toxicity will be reported by short name, type, grade, and attribution as per CTCAE v4.0.3.

The exploratory endpoints include:

- The quantity of CD3+ T-cells in peripheral blood and in tumor biopsies at each timepoint (baseline, cycle 3, and off-study).
- The expression category in tumor tissue (none (0%), low (<5%), intermediate (5-50%), or high (>50%) of various markers including PD-1, PD-L1, PD-L2, CTLA-4, TIM-3, LAG-3 at each timepoint (baseline, cycle 3, and off-study).
- The following T cell subsets will be studied in peripheral blood and tumor tissue: (CD4, CD8, T-reg, CTLA4, TIM3, LAG3, memory, naïve, PD-1, Ki67). For each marker, the absolute change in the marker(s) value will be calculated:
  - Cycle 3 marker value minus Baseline marker value
  - Progression marker value minus Cycle 3 marker value
  - Progression marker value minus Baseline marker value
- For each of the alternative (non-RECIST) radiological measurements we will categorize tumor response as CR/PR/SD vs PD. CT and/or MRI with dynamic contrast enhanced sequences will be collected throughout the study at every disease evaluation and analyzed using Choi criteria, MRI volumetrics, and

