#### Analysis for Primary Endpoint

The primary endpoint is progression-free survival (PFS) by RECIST 1.1 in evaluable patients treated with combination axitinib/pembrolizumab. PFS will be analyzed by Kaplan-Meier (KM) methods, and point estimates and 2-sided 95% confidence intervals for PFS will be reported for selected times such as 3, 6 and 12 months from treatment start using Greenwood's variance and the log-log transform method. Median PFS time, if attained, will also be reported.

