#### Analysis for Secondary Endpoints

Objective response (CR or PR) and best response (CR, PR, or SD) by RECIST 1.1 to axitinib/pembrolizumab combination therapy will be tabulated, summarized and reported with 95% confidence intervals. Overall survival will be analyzed by Kaplan-Meier (KM) curves with standard error according to Greenwood's variance and the log-log transform method. Median OS will be reported if attained.

Toxicity will be summarized by reporting the number of patients treated, the number who experience DLT, SAEs and grade 3 or higher AE, the proportion of patients treated at various axitinib dose titration levels, the number of patients who discontinue therapy, and the reasons for discontinuation. Comprehensive safety data on all grade 3 and 4 toxicities will be tabulated by type, grade, duration, attribution to treatment, and dose level received.

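### The primary PFS set leaves out patients who die or fail early, although the plan's own PFS definition counts those deaths as events, and the efficacy sets conflict

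*Combined protocol and SAP*

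**What the plan says.** - **Primary endpoint.** Section 3.1 admits eligible subjects who "received 80% of scheduled axitinib doses and two infusions of pembrolizumab, have measurable disease at baseline and at least one post-baseline disease assessment". It gives no period for the 80%. The nearest period, weeks 1 to 4, appears in 14.1.1 and only for toxicity.
- **Use in the analysis.** Section 16.2 (Endpoints): "The primary endpoint will be the progression-free survival by RECIST 1.1 in evaluable patients treated with combination axitinib/pembrolizumab". Section 16.3 names the same population: "progression-free survival (PFS) by RECIST 1.1 in evaluable patients treated with combination axitinib/pembrolizumab".
- **PFS definition.** Section 14.2: "PFS is defined as the time from treatment initiation until documented disease progression or death (by any cause, in the absence of progression". Patients without progression are censored at their last evaluable tumour assessment.
- **Secondary endpoints.** Section 3.2 applies the filter to response, clinical benefit, TTP and OS, requiring patients who "received at least 80% of scheduled axitinib doses and two infusions of pembrolizumab" and have a post-baseline assessment. Section 16.3 says only "Overall survival will be analyzed by Kaplan-Meier (KM) curves with standard error" and so on, with no such restriction for OS.
- **Other sets.** Section 16.2 (Analysis set) repeats the exposure rule but labels it for treatment response. Section 16.2 (Exclusions) removes cycle 1 drop-outs from efficacy endpoints unless the reason is DLT or clinical progression. Section 14.1.1, for objective response, asks for one cycle and a re-evaluation, and keeps objective progression before the end of cycle 1.
- **Timing.** Section 8.0 gives pembrolizumab on days 8 and 29 of cycle 1. Section 14.1 schedules response assessment every 12 weeks from enrolment.
- **Hypothesis.** Section 16.4 plans 40 evaluable patients and tests a 3-month PFS of 19% against 40%, one-sided 5%, with 97.5% power.

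**The concern.** Entry to the primary set depends partly on the outcome being measured. To qualify, a patient must reach the second infusion and have a disease assessment, and the first scheduled one falls close to the 3-month landmark. Deaths and failures before then are the events that a 3-month PFS rate should count.

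The resulting rate is set against a 19% historical figure, so a set cleared of early failures is likely to look better than the treated population did. Response and clinical benefit carry the same filter, and so does OS if section 3.2 governs. Because 3.1 and 16.2 (Exclusions) are not reconciled, and the response sets differ as well, two analysts could build different efficacy sets from the same data.

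**Working it through.** **1. The plan's power figure.** Assuming exponential PFS, the monthly hazards are −ln(0.19)/3 = 0.5536 and −ln(0.40)/3 = 0.3054, a ratio of 0.552. With 15 months of accrual and 12 of follow-up, the event probability under the alternative is 0.994, so about 39.8 events from 40 patients. Power on the log-hazard scale is Φ(√39.8 × 0.595 − 1.645) = Φ(2.11) = 98.2%. A simulated one-sample log-rank test gives 97.3%. The stated 97.5% is reproduced; the power is not the fault.

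**2. The rules side by side.**

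| Patient | 14.2 (PFS) | 3.1 set | 16.2 Exclusions |
|---|---|---|---|
| Dies on day 20, no assessment | Event on day 20 | Out | Death is not a named exception |
| Two infusions, dies in week 10, no assessment | Event | Out | Not excluded |
| Leaves for DLT before day 29 | Followed for PFS | Out (one infusion) | Kept |
| Leaves for clinical progression before day 29 | Event if progression is documented | Out | Kept |
| Completes cycle 1, alive, never re-assessed | Censored at the screening scan | Out | Not excluded |

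In the last row the censoring rule fails. Screening scans may be taken up to 28 "days prior to Cycle 1, day 1 of treatment" (12.1), so the censoring time is at or before zero.

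**3. Effect on the 3-month rate.** Let p be the true rate in all treated patients, f the share excluded, and g the share of excluded patients who failed by 3 months.

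Rate in the evaluable set = (p − f(1 − g)) / (1 − f)

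The documents do not give f or g; both are assumptions.

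| p | g | f = 5% | f = 10% |
|---|---|---|---|
| 19% | 100% | 0.19/0.95 = 20.0% | 0.19/0.90 = 21.1% |
| 19% | 90% | 0.185/0.95 = 19.5% | 0.18/0.90 = 20.0% |
| 19% | 70% | 0.175/0.95 = 18.4% | 0.16/0.90 = 17.8% |
| 40% | 100% | 0.40/0.95 = 42.1% | 0.40/0.90 = 44.4% |

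The bias is zero when g = 1 − p: 81% failed at a true 19%, 60% at a true 40%. Below that it reverses.

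**4. What an observed result would leave open.** Suppose 16 of 40 evaluable patients (40%) are progression-free at 3 months.
- 2 excluded: the all-treated rate lies between 16/42 = 38.1% and 18/42 = 42.9%.
- 4 excluded: between 16/44 = 36.4% and 20/44 = 45.5%.

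**5. Type I error.** The one-sample log-rank test was simulated at a true all-treated rate of 19%, with 40 evaluable patients still reached and every excluded patient an early event. The rejection rate was 3.6% at f = 0, 5.0% at 5%, 6.8% at 10% and 9.1% at 15%, against a nominal 5%. These are upper-side figures because they take g = 100%.

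**6. Plausible size of f.** None of these fixes it.
- Section 1.1 cites a median OS of 12 to 18 months. With exponential survival (an assumption), the share dead by time t is 1 − 2^(−t/median). By day 29 (0.95 months) this is 5.4% to 3.6%; by week 12 (2.76 months), 14.7% to 10.1%. Patients assessed before death would still qualify on that condition.
- The synopsis expects 45 patients, including screen failures and non-evaluable patients, against 40 evaluable. If 45 is the whole total, at most 5/45 = 11.1% are non-evaluable.
- Section 1.5 reports 10 evaluable of 12 ASPS patients, so at most 2/12 = 16.7%. One had not reached 3 months, and the rule used is not stated.

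**The case against.** The strongest reply is that the restriction is openly pre-specified in a single-arm phase II trial whose stated aim is estimation, and that the likely shift is small: one to two points at 19% under the least favourable assumption with f of 5% to 10%, against a 19% versus 40% contrast. The direction is not certain either, since the 80% rule can also remove progression-free patients whose axitinib was held or stopped for toxicity.

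Several narrower points are fair:
- Section 16.2 (Exclusions) keeps some cycle 1 failures, so not every reading of the plan drops them. It does not name death as an exception, however, and it contradicts 3.1.
- Section 14.1.1 defines a response set. Its conflict is with 3.2 and the 16.2 analysis set, not with the PFS set.
- Section 3.1 asks for a disease assessment, and clinical lesions may be measured by calipers, so some patients could qualify before week 12. Off-treatment and follow-up imaging (12.3, 12.5) will also bring in some early stops. The loss is mainly deaths before an assessment or the second infusion, missed assessments, and stops below the exposure limits.
- The censoring gap does not arise inside the 3.1 set, which already excludes unassessed patients. It matters once the set is widened.
- The OS restriction holds only if 3.2 overrides 16.3.

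These points limit the size and reach of the problem. They do not remove the contradiction between 3.1 and 14.2, and they do not supply an all-treated analysis.

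**Conclusion.** The point holds and should be fixed before the primary analysis. Followed as written, section 3.1 removes deaths that section 14.2 counts as PFS events, no all-treated efficacy analysis is stated, and no text says which efficacy set governs.

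The probable effect is a modest upward bias. With 5% to 10% of treated patients excluded, all of them failures, it is 1.0 to 2.1 percentage points at a true 19% and 2.1 to 4.4 at a true 40%; simulated type I error is 5.0% to 6.8%, compared with 3.6% without exclusions. The size rests on assumed values of f and g, and the sign reverses if fewer than 81% (at 19%) or 60% (at 40%) of excluded patients failed. The conflict between the definitions does not depend on those assumptions.

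**What to change.** 1. Make the primary PFS set all eligible patients who started study treatment. List any treated patient later judged ineligible, with the reason.
2. Count a death before the first post-baseline assessment as a PFS event on the date of death.
3. State how living patients with no post-baseline assessment are handled, since 14.2 would censor them at or before time zero. Report their number, and add an analysis counting them, and patients with symptomatic deterioration without RECIST documentation (note to Table 14), as failures at 3 months.
4. Keep the 80%/two-infusion set as a sensitivity analysis and state the period over which the 80% is counted.
5. For ORR and CBR, count patients with no post-baseline assessment as non-responders and as without clinical benefit. Analyse OS in all treated patients.
6. Use consistent definitions in 3.1, 3.2, 14.1.1 and 16.2, including the Exclusions paragraph.
7. Because some ASPS outcomes have already been reviewed (1.5), record the change and its reason in a dated amendment and report both sets.

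The cost is an amendment to the wording and a second run of the same analyses on data already collected. Reported PFS, ORR, CBR and OS may be somewhat lower.

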### 3.2 Secondary endpoints

- The objective response (CR/PR), clinical benefit (CR/PR/SD), time to progression (TTP), and overall survival (OS) defined as time from study treatment initiation to first occurrence of progression by RECIST v1.1 or death of sarcoma patients treated with concurrent axitinib/pembrolizumab therapy.

Evaluable criteria:

Eligible subjects enrolled into the study that received at least 80% of scheduled axitinib doses and two infusions of pembrolizumab, have measurable disease at baseline and at least one post-baseline disease assessment.

- Adverse events, including dose-limiting toxicity and serious adverse events (grade 3 or 4) will be graded using NCI CTCAE version 4.03.

Evaluable criteria:

Eligible subjects enrolled into the study that receive at least one dose of both axitinib and pembrolizumab. Patients who withdraw from the study prior to week 2 for any reason other than DLT or other significant toxicity will not be considered evaluable for toxicity.

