### 15.3 Serious Adverse Events (see also Appendix A)

Serious AE (SAE) means any untoward medical occurrence that occurs at any dose:

1. Results in death.
2. Is life-threatening.

The term "life-threatening" in the definition of "serious" refers to an event in which the patient was at risk of death at the time of the event; it does not refer to an event which hypothetically might have caused death if it were more severe).

3. Requires inpatient hospitalization or prolongation of present hospitalization.

Elective hospitalization to simplify protocol treatment/evaluations or to treat a baseline condition that did not worsen from baseline will not be considered an SAE.

4. Results in persistent or significant disability/incapacity.  
Disability is defined as a substantial disruption of a person's ability to conduct normal life functions.
5. Is a congenital anomaly/birth defect.
6. Is a medically important event.  
A medically important event may not be immediately life threatening or result in death or hospitalization but may jeopardize the patient or may require intervention to prevent one of the other outcomes listed in the definition above, or involves suspected transmission via a medicinal product of an infectious agent. Examples of such medical events include allergic bronchospasm requiring intensive treatment in an emergency room or at home, blood dyscrasias or convulsions that do not result in inpatient hospitalization, or the development of drug dependency or drug abuse; any organism, virus, or infectious particle (e.g., prion protein transmitting Transmissible Spongiform Encephalopathy), pathogenic or nonpathogenic, is considered an infectious agent.

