**Additional SAE classification(s) for AEs occurring at any dose or during any use of Merck product(s):**

6. Is a new cancer (that is not a condition of the study);
7. Is associated with an overdose (whether accidental or intentional): Any adverse event associated with an overdose is considered a serious adverse event. An overdose that is not associated with an adverse event is considered a non-serious event of clinical interest and must be reported within 24 hours.
8. Is another important medical event

Clarification should be made between the terms *serious* and *severe* because they ARE NOT synonymous. The term *severe* is often used to describe the intensity (severity) of a specific event (as in mild, moderate, or severe myocardial infarction); the event itself, however, may be of relatively minor medical significance (such as a severe headache). This is NOT the same as *serious*, which is based on patient/event outcome or action criteria described above and is usually associated with events that pose a threat to a patient's life or functioning. A severe AE does not necessarily need to be considered serious. For example, persistent nausea of several hours duration may be considered severe nausea but not an SAE. On the other hand, a stroke resulting in only a minor degree of disability may be considered mild but would be defined as an SAE based on the above noted criteria. Seriousness (not severity) serves as a guide for defining regulatory reporting obligations.

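### The safety endpoint labels serious adverse events as grade 3 or 4, against Section 15.3, and the detailed toxicity table stops at grade 4, so no planned output specifies duration or axitinib dose level for fatal toxicities or serious grade 1-2 events

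*Combined protocol and SAP*

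**What the plan says.** The safety endpoint appears twice. Section 3.2 has "Adverse events, including dose-limiting toxicity and serious adverse events (grade 3 or 4) will be graded using NCI CTCAE version 4.03". Section 16.2, under Endpoints, has "Adverse events, including dose-limiting toxicity and grade 3 or grade 4 serious adverse events". A sub-bullet there describes DLTs as treatment-related "grade 3 or higher toxicities as detailed in section 7.2" and adds that toxicity will be reported with its CTCAE short name, type, grade and attribution.

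Section 15.3 defines the term differently: "Serious AE (SAE) means any untoward medical occurrence that occurs at any dose", followed by a list of outcomes. Death comes first, and another criterion is "Requires inpatient hospitalization or prolongation of present hospitalization". The section warns that serious and severe are different things: "A severe AE does not necessarily need to be considered serious". It also gives the converse, a stroke that is mild in grade but serious by outcome.

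Section 16.3, Analysis for Secondary Endpoints, plans two kinds of output. One is a set of patient counts, including "the number who experience DLT, SAEs and grade 3 or higher AE", together with the share of patients at each axitinib titration level and the reasons for stopping therapy. The other is a detailed table: "Comprehensive safety data on all grade 3 and 4 toxicities will be tabulated by type, grade, duration, attribution to treatment, and dose level received".

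**The concern.** The endpoint wording ties seriousness to a band of CTCAE grades, whereas the protocol's own definition ties it to outcome. By grade, the label leaves out two groups that Section 15.3 includes: fatal events (grade 5), and events of grade 1 or 2 that are serious because, for example, the patient was hospitalized. The detailed table then leaves out the same two groups.

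Describing the safety of titrated axitinib with pembrolizumab is a secondary objective (Section 2.2), and Table 3 allows axitinib to range from 2 mg to 10 mg twice daily. The detailed table is the planned output that connects an event to the drug and to the dose level received. If it is produced exactly as written, the gravest events are missing from the place where a reader would look for that connection.

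**Working it through.** The plan gives no figure to reproduce and no calculation decides the point. The check is to follow each kind of event through the planned outputs.

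| Event | SAE label in 3.2 and 16.2 | Patient counts in 16.3 | Detailed table in 16.3 | Type and attribution line in 16.2 |
|---|---|---|---|---|
| Grade 3-4, serious | inside | counted | included | covered if a DLT; otherwise depends on reading |
| Grade 3-4, not serious | not applicable | counted | included | covered if a DLT; otherwise depends on reading |
| Grade 5 toxicity | outside | counted, as an AE of grade 3 or above and, under 15.3, as an SAE | not included | covered if a DLT; otherwise depends on reading |
| Grade 1-2, serious | outside | counted if 15.3 governs; lost if the endpoint label is carried over | not included | depends on reading |

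Step by step:

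1. **Which SAE definition governs the count.** The SAE count in Section 16.3 carries no grade qualifier. Section 15.5 requires each event to be recorded as serious or not according to Section 15.3. Sections 3.2 and 16.2 nevertheless define the endpoint being analyzed and carry the qualifier. Nothing states which prevails.

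2. **Fatal events in the counts.** The other count has a lower bound of grade 3 and no upper bound, so grade 5 is in it. It does not show grade 5 separately.

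3. **The detailed table.** It has five descriptors: type, grade, duration, attribution and dose level. Its scope is grades 3 and 4, although the preceding sentence in the same paragraph uses grade 3 and above.

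4. **What the Section 16.2 line can supply.** It offers type, grade and attribution, but not duration or dose level. On the wide reading, the two uncapped event groups therefore lack 2 of the 5 descriptors. On the narrow reading it covers DLTs only. Section 7.2 confines DLTs to the first cycle (49 days) and to events considered related, and Section 16.2 describes them as grade 3 or higher. A serious grade 1-2 event, or a fatal toxicity after cycle 1, then has none of the five specified. Section 8.0 permits no axitinib escalation during cycle 1, so the narrow reading does not reach events that arise after escalation.

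5. **Dose level elsewhere.** The share of patients at each titration level describes exposure. It does not link an event to a dose.

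Some figures give scale but serve as illustration only. One death among the 40 evaluable patients in Section 16.4 is 1/40 = 2.5%, which is conditional on a death occurring and is not an estimate of risk. Section 9.1.4 cites axitinib fatalities of 1/359 each for stroke, pulmonary embolism and hemorrhage, in renal cell carcinoma. Section 9.2.4 reports 12 pneumonitis cases in 411 melanoma patients, of which 8 were grade 2. It does not say that any grade 2 case was serious.

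**The case against.** The best reply is that little is lost. Both endpoint statements list DLTs and SAEs as things that adverse events include, so the endpoint remains all adverse events and the grade label is loose wording. Section 16.3 counts SAEs without a grade limit and AEs of grade 3 or above. Section 15.6 puts every AE on the case report form. Section 17.0 suspends enrollment after a treatment-related death, so such a death could not go unnoticed.

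Most of this stands, and it rules out three stronger readings. A reader might infer that fatal and serious low-grade events fall outside the safety results altogether. The documents do not support that, because the counts take in fatal events and, under Section 15.3, serious events of any grade. A reader might also infer that a fatal toxicity is never shown by type or attribution. The Section 16.2 line does so for any fatal DLT, and for every toxicity on its wide reading. Finally, a reader might infer that SAE counts will differ between the safety database and the analysis. That happens only if an analyst carries the endpoint label into the count.

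The reply does not touch the table. Data collection and committee review are not planned analyses, and neither commits the sponsor to reporting these events by duration and dose level.

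**Conclusion.** The point holds in limited form. The grade label in Sections 3.2 and 16.2 contradicts Section 15.3 and leaves the SAE count open to two readings. The detailed table, followed literally, omits grade 5 toxicities and serious grade 1-2 events. For these, duration and axitinib dose level are specified nowhere, and type and attribution depend on how one line in Section 16.2 is read.

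The size cannot be put as a number. The documents give no rate of serious grade 1-2 events, and whether any death occurs is unknown. The primary endpoint, the stopping guideline and the collected data are unaffected. The correction should still be made, because it changes the content of the main safety table for a secondary objective. The conclusion assumes that the table will be produced as worded; an analyst who silently widened it would avoid the gap.

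**What to change.** - In Sections 3.2 and 16.2, replace the grade-limited phrase with: serious adverse events of any grade as defined in Section 15.3, and grade 3 to 5 adverse events.
- In Section 16.3, widen the scope of the detailed table to: all grade 3 to 5 toxicities and all SAEs of any grade. Keep the same columns.

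The cost is three wording changes and a few more rows. Section 15.5 already lists onset and resolution dates, grade, relationship, seriousness and outcome for each event, and axitinib dosing is recorded in the diary (Section 8.5.1). No new data collection is needed, and nothing in dosing or clinical management changes.
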